### **12.3.2.2 Change from baseline in the average AM iTNSS over the first 6, 30 and 52 weeks of treatment**

AM iTNSS will be analyzed using same methods as described in Section [12.3.2.1](#).

The efficacy endpoints iTNSS will be analyzed using a mixed model repeated measures model, adjusting for covariates that include treatment, site, baseline and week as the within-subject effect (for both the FAS and the PPS). The interactions of site-by-treatment and baseline-by-treatment will be investigated separately in the model and will only be included in final model if they are statistically significant at the  $\alpha=5\%$  level. An unstructured (UN) covariance will be assumed. If the model does not converge using the unstructured covariance structure, the autoregressive (order 1) AR(1) structure will be used. If this also does not converge other covariance structures deemed appropriate to fit the data will be used. This method will assume that any missing data is Missing at Random (MAR). The statements of a

|  |                                    |                                  |
|--|------------------------------------|----------------------------------|
| Protocol Number:
GPL/CT/2014/018/III
(Study No. GSP 301-303) | SAP Version Number:
Version 1.0 | SAP Version Date:
04-Apr-2017 |
|--|------------------------------------|----------------------------------|

SAS PROC MIXED analysis would be (if the interactions of treatment\*baseline and treatment\*site is not statistically significant):

```
proc mixed;
class subject treatment site week;
model change = treatment site baseline week;
repeated week / subject = subject type=UN;
lsmeans treatment / cl diff e ;
ods output lsmeans=lsmeans ;
ods output diffs=diffs ;
run ; quit ;
```

The adjusted means for each treatment and the estimated treatment differences for the treatment comparisons will be presented together with 95% confidence intervals for the differences and p-values for the treatment comparisons. The adjusted means and estimated treatment differences for the treatment comparisons will also be plotted, with corresponding 95% confidence intervals.

The responses for the first 6, 30 and 52 weeks of treatment will all be analysed in separate statistical models.

A multiple, imputation-based approach may be considered for handling missing data for AM iTNSS upon review of amount of missing data observed.

**12.3.2.3 Change from baseline in the overall RQLQ(S) score at Weeks 6, 30, and 52**

RQLQ(S) (for the FAS) will be analyzed using similar methods as described in Section [12.3.2.1](#), with the following differences:

- Interaction of week-by-treatment will be included in the statistical model
  - Addition of week\*treatment interaction in SAS model statement
  - Week\*treatment interaction stated in SAS lsmeans statement
- The responses at 6, 30 and 52 weeks of treatment will all be analysed in the same statistical model.

The interactions of site-by-treatment and baseline-by-treatment will be investigated separately in the model and will only be included in final model if they are statistically significant at the alpha=5% level. An unstructured (UN) covariance will be assumed. If the model does not converge using the unstructured covariance structure, the autoregressive (order 1) AR(1) structure will be used. If this also does not converge other covariance structures deemed appropriate to fit the data will be used.

For each visit, the adjusted means for each treatment and the estimated treatment differences for the treatment comparisons will be presented together with 95% confidence intervals for the differences and p-values for the treatment comparisons.

|  |                                    |                                  |
|--|------------------------------------|----------------------------------|
| Protocol Number:
GPL/CT/2014/018/III
(Study No. GSP 301-303) | SAP Version Number:
Version 1.0 | SAP Version Date:
04-Apr-2017 |
|--|------------------------------------|----------------------------------|

The adjusted means and estimated treatment differences for the treatment comparisons will also be plotted, with corresponding 95% confidence intervals.

### 12.3.6 Examination of Subgroups

As well as producing summary tables for the efficacy endpoints rTNSS and iTNSS, the following subgroups of clinical interest will also be summarized for the FAS only by treatment group and week: age group (12-17, 18-65, 65 and above), sex (female/male), race (American Indian or Alaska Native, Asian, Black/African American, Other and White) and ethnicity (Hispanic or Latino and Not Hispanic or Latino).

## 12.4 Efficacy Analyses of Other Efficacy Endpoints

### 12.4.1 Overview of Analysis of the Other Efficacy Endpoints

The efficacy analysis of the other efficacy endpoints will be performed on the FAS only, unless otherwise specified. For RQLQ(S) certain outputs will also be performed on the RQLQ(S) analysis set. The interaction of site-by-treatment and baseline-by-treatment will not be investigated for the other efficacy endpoints.

Efficacy analyses of other efficacy endpoints include the following:

#### Nasal symptoms:

- Change from baseline in the average AM subject-reported reflective individual nasal symptoms over the first 6, 30, and 52 weeks of treatment.
- Change from baseline in the average AM subject-reported instantaneous individual nasal symptoms over the first 6, 30, and 52 weeks of treatment.
- Change in the average AM subject-reported rTNSS and iTNSS from baseline to the end of each treatment week.
- Change in the average AM subject-reported reflective individual nasal symptoms from baseline to the end of each treatment week.
- Change in the average AM subject-reported instantaneous individual nasal symptoms from baseline to the end of each treatment week.

#### Physician assessed Nasal Symptom Score (PNSS), Rhinoconjunctivitis Quality of Life Questionnaire – Standardized Activities (RQLQ(S)), and Rhinitis Control Assessment Test (RCAT):

- Change from baseline in PNSS and physician assessed individual nasal symptoms at Weeks 6, 30, and 52.
- Change from baseline in individual domains of the RQLQ(S) at Weeks 6, 30, and 52 for the FAS.

## STATISTICAL ANALYSIS PLAN

|  |                                    |                                  |
|--|------------------------------------|----------------------------------|
| Protocol Number:
GPL/CT/2014/018/III
(Study No. GSP 301-303) | SAP Version Number:
Version 1.0 | SAP Version Date:
04-Apr-2017 |
|--|------------------------------------|----------------------------------|

- Change from baseline in overall RQLQ(S) score and individual domains of the RQLQ(S) at Weeks 6, 30, and 52 for the RQLQ(S) Analysis Set.
- Change from baseline in the RCAT at Weeks 6, 30, and 52.
- Change from baseline in individual domains of the RCAT at Weeks 6, 30, and 52.

[Table 4](#) provides an overview of the planned efficacy analyses.

|  |                                    |                                  |
|--|------------------------------------|----------------------------------|
| Protocol Number:
GPL/CT/2014/018/III
(Study No. GSP 301-303) | SAP Version Number:
Version 1.0 | SAP Version Date:
04-Apr-2017 |
|--|------------------------------------|----------------------------------|

**Table 4: Overview of Planned Efficacy Analyses for Other Efficacy Endpoints**

|   | Stats Analysis |   | Summary |   | Individual |
|---|----------------|---|---------|---|------------|
|   | T              | F | T       | F | L          |
| Change from baseline in the average AM reflective individual nasal symptoms over the first 6, 30, and 52 weeks of treatment             |                |   |         |   |            |
| MMRM – FAS  | Y              |   |         |   | Y          |
| Change from baseline in the average AM instantaneous individual nasal symptoms over the first 6, 30, and 52 weeks of treatment          |                |   |         |   |            |
| MMRM – FAS  | Y              |   |         |   | Y          |
| Change in the average AM subject-reported rTNSS and iTNSS from baseline to the end of each treatment week                               |                |   |         |   |            |
| rTNSS – MMRM – FAS  | Y              |   | Y       |   | Y          |
| rTNSS - PPS   |                |   | Y       |   |            |
| iTNSS – MMRM – FAS  | Y              |   | Y       |   | Y          |
| iTNSS - PPS   |                |   | Y       |   |            |
| Change in the average AM reflective individual nasal symptoms from baseline to the end of each treatment week                           |                |   |         |   |            |
| MMRM – FAS  | Y              |   | Y       |   | Y          |
| Change in the average AM instantaneous individual nasal symptoms from baseline to the end of each treatment week                        |                |   |         |   |            |
| MMRM – FAS  | Y              |   | Y       |   | Y          |
| Change from baseline in PNSS and physician assessed individual nasal symptoms at Weeks 6, 30, and 52                                    |                |   |         |   |            |
| MMRM – FAS  | Y              |   | Y       |   | Y          |
| Change from baseline in individual domains of the RQLQ(S) at Weeks 6, 30, and 52 for the FAS  |                |   |         |   |            |
| MMRM – FAS  | Y              |   | Y       |   | Y          |
| Change from baseline in overall RQLQ(S) score and individual domains of the RQLQ(S) at Weeks 6, 30, and 52 for the RQLQ(S) Analysis Set |                |   |         |   |            |
| MMRM – RQLQ analysis set  | Y              |   | Y       |   |            |
| Change from baseline in the RCAT at Weeks 6, 30, and 52   |                |   |         |   |            |
| MMRM – FAS  | Y              |   | Y       |   | Y          |
| Change from baseline in individual domains of the RCAT at Weeks 6, 30, and 52   |                |   |         |   |            |
| MMRM – FAS  | Y              |   | Y       |   | Y          |

**NOTES :**

- T = Table, F = Figure, L = Listing, Y = Yes display generated.
- Stats Analysis = Represents TF related to any formal statistical analyses (i.e. modeling) conducted.
- Summary = Represents TF related to summaries (i.e. descriptive statistics) of the baseline, post-treatment and change from baseline for the primary efficacy analyses method.
- Individual = Represents L related to any displays of individual subject observed raw data.

|  |                                    |                                  |
|--|------------------------------------|----------------------------------|
| Protocol Number:
GPL/CT/2014/018/III
(Study No. GSP 301-303) | SAP Version Number:
Version 1.0 | SAP Version Date:
04-Apr-2017 |
|--|------------------------------------|----------------------------------|

**12.4.2 Analysis of Change from Baseline in Other Efficacy Endpoints**

**12.4.2.1 Change from baseline in the average AM reflective and AM instantaneous individual nasal symptoms over the first 6, 30, and 52 weeks of treatment**

Similar to the analysis mentioned in section [12.3.2.1](#), the endpoints will be analyzed separately using a mixed model repeated measures model (by each individual nasal symptom), adjusting for covariates that include treatment, site, baseline and week as the within-subject effect (for the FAS). An unstructured (UN) covariance will be assumed. If the model does not converge using the unstructured covariance structure, the autoregressive (order 1) AR(1) structure will be used. If this also does not converge other covariance structures deemed appropriate to fit the data will be used. The statements of a SAS PROC MIXED analysis would be:

```
proc mixed;
by individual nasal symptom;
class subject treatment site week;
model change = treatment site baseline week;
repeated week / subject = subject type=UN;
lsmeans treatment / cl diff e ;
ods output lsmeans=lsmeans ;
ods output diffs=diffs ;
run ; quit ;
```

For each individual nasal symptom, the adjusted means for each treatment and the estimated treatment differences for the treatment comparisons will be presented together with 95% confidence intervals for the differences and p-values for the treatment comparisons. The adjusted means and estimated treatment differences for the treatment comparisons will also be plotted, with corresponding 95% confidence intervals.

The responses for the first 6, 30 and 52 weeks of treatment will all be analysed in separate statistical models.

**12.4.2.2 Change in the average AM subject-reported rTNSS and iTNSS from baseline to the end of each treatment week**

The efficacy endpoints rTNSS and iTNSS will be analyzed separately using a mixed model repeated measures model, adjusting for covariates that include treatment, site, baseline and week as the within-subject effect, and the model will include treatment\*week interaction term (for the FAS). The statements of a SAS PROC MIXED analysis would be:

```
proc mixed;
```

|  |                                    |                                  |
|--|------------------------------------|----------------------------------|
| Protocol Number:
GPL/CT/2014/018/III
(Study No. GSP 301-303) | SAP Version Number:
Version 1.0 | SAP Version Date:
04-Apr-2017 |
|--|------------------------------------|----------------------------------|

```
class subject treatment site week;
model change = treatment site baseline week treatment*week;
repeated week / subject = subject type=UN;
lsmeans treatment treatment*week / cl diff e ;
ods output lsmeans=lsmeans ;
ods output diffs=diffs ;
run ; quit ;
```

For each week, the adjusted means for each treatment and the estimated treatment differences for the treatment comparisons will be presented together with 95% confidence intervals for the differences and p-values for the treatment comparisons. The adjusted means and estimated treatment differences for the treatment comparisons will also be plotted, with corresponding 95% confidence intervals.

Descriptive statistics (number of subjects, mean, standard deviation, median, minimum and maximum) will be provided for baseline, post treatment and change from baseline by treatment group and week (for both the FAS and the PPS).

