## 1.0 Changes to the Protocol Defined Statistical Analysis Plan

- The protocol states that the efficacy analysis will be conducted using an analysis of covariance (ANCOVA) model (adjusting for study treatment group, site and baseline). The efficacy analysis will now be analyzed using a mixed models repeated measures (MMRM) model. This will be more applicable to the design of the study, and assesses missing data using the Missing at Random (MAR) assumption. More detail is in Section [12.3](#).
- The protocol states that ‘A multiple, imputation-based approach where complete data sets are drawn will be used for handling missing data in the efficacy analysis.’ Because assessing efficacy is a secondary objective of the study, the sentence has been modified to state ‘A multiple, imputation-based approach *may* be considered for handling missing data for AM reflective Total Nasal Symptom Score (rTNSS) and AM instantaneous Total Nasal Symptom Score (iTNSS) upon review of amount of missing data observed’. More details in Section [12.3](#).
- The protocol states that the computer-generated randomization scheme will be reviewed and approved by an independent statistician and the randomization will be stratified by site. This was inaccurately stated. The computer-generated randomization scheme will be reviewed and approved by a statistician and the randomization will not be stratified by site. More detail is in Section [7.0](#).
- The protocol has defined the Full Analysis Set (FAS) as ‘The FAS will consist of all subjects who are randomized and received at least 1 dose of Investigational Product (IP) and have at least 1 post-baseline efficacy assessment.’ To add more clarity the definition of the FAS is ‘The FAS will consist of all subjects who are randomized and received at least 1 dose of IP and have at least 1 post-baseline AM rTNSS assessment.’

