## 8.0 Sample Size Determination

The sample size of 600 subjects for this study (400 subjects on GSP 301 NS and 100 subjects in each of the 2 placebo groups) is based on the ICH E1 Guideline (ICH E1) and the FDA Guidance on Allergic Rhinitis which requires treatment of at least 300 subjects for 6 months and 100 subjects for 1 year. Based on an estimated attrition rate of 25% after 6 months and 50% after 52 weeks, 400 subjects in the GSP 301 NS treatment group are considered sufficient to meet the above requirements.

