## STATISTICAL ANALYSIS PLAN

|  |                                    |                                  |
|--|------------------------------------|----------------------------------|
| Protocol Number:
GPL/CT/2014/018/III
(Study No. GSP 301-303) | SAP Version Number:
Version 1.0 | SAP Version Date:
04-Apr-2017 |
|--|------------------------------------|----------------------------------|

site-by-treatment and baseline-by-treatment will be investigated separately in the model and will only be included in final model if they are statistically significant at the  $\alpha=5\%$  level. An unstructured (UN) covariance will be assumed. If the model does not converge using the unstructured covariance structure, the autoregressive (order 1) AR(1) structure will be used. If this also does not converge other covariance structures deemed appropriate to fit the data will be used. This method will assume that any missing data is Missing at Random (MAR). The statements of a SAS PROC MIXED analysis would be (if the interactions of treatment\*baseline and treatment\*site is not statistically significant):

```
proc mixed;  
class subject treatment site week;  
model change = treatment site baseline week;  
repeated week / subject = subject type=UN;  
lsmeans treatment / cl diff e ;  
ods output lsmeans=lsmeans ;  
ods output diffs=diffs ;  
run ; quit ;
```

The adjusted means for each treatment and the estimated treatment differences for the treatment comparisons will be presented together with 95% confidence intervals for the differences and p-values for the treatment comparisons. The adjusted means and estimated treatment differences for the treatment comparisons will also be plotted, with corresponding 95% confidence intervals.

The responses for the first 6, 30 and 52 weeks of treatment will all be analysed in separate statistical models.

A multiple, imputation-based approach may be considered for handling missing data for AM rTNSS upon review of amount of missing data observed.

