**12.4.2.4 Change from baseline in PNSS, Overall RQLQ(S) score and RCAT at Weeks 6, 30, and 52**

RQLQ(S) (for RQLQ(S) Analysis Set), PNSS (for FAS) and RCAT (for FAS) will be analyzed separately using the same methods as described in Section 12.3.2.2 with the exception that the interaction of site-by-treatment and baseline-by-treatment will not be investigated separately in the model.

**12.4.2.5 Change from baseline in physician assessed individual nasal symptoms, individual domains of the RQLQ(S) and individual domains of the RCAT at Weeks 6, 30, and 52**

RQLQ(S) (for both the FAS and RQLQ(S) Analysis Set), PNSS (for FAS) and RCAT (for FAS) will be analyzed separately using the same methods as described in Section 12.4.2.4, with the addition of a by statement (for the individual symptoms/domains) in the SAS PROC MIXED model.

|   |   |   |
|---|---|---|
|  | STATISTICAL ANALYSIS PLAN          |   |
| Protocol Number:
GPL/CT/2014/018/III
(Study No. GSP 301-303)         | SAP Version Number:
Version 1.0 | SAP Version Date:
04-Apr-2017 |

### Appendix 1

The following shells are provided in order to provide a framework for the display of data from this study. These shells may not be reflective of every aspect of this study but are intended to show the general layout of the Tables, Listings and Figures that will be included in the final clinical study report. Tables, Listings and Figures are numbered following the ICH structure. Table headers, variables names and footnotes will be modified as needed following data analyses. Additional Tables, Listings and Figures will be generated, as needed, following the data analysis (post-hoc). All descriptive and inferential statistical analyses will be performed using SAS® statistical software Version 9.4 or later, unless otherwise noted. In general, Listings will be sorted and presented by treatment and subject number. Subject number when broken down consists of the Site Number and Subject Number.

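### The by-week and by-visit MMRMs assume one baseline slope for all weeks; if the slope changes and dropout leaves the arms with different baseline mixes, late-week differences can be biased in either direction, so add baseline*week

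*SAP*

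**What the plan says.** The weekly rTNSS and iTNSS model in SAP 12.4.2.2 is "model change = treatment site baseline week treatment*week". SAP 12.4.2.3 uses the same statement for each individual symptom. For overall RQLQ(S) at Weeks 6, 30 and 52, SAP 12.3.2.3 takes the 12.3.2.1 code, which has one baseline term, and changes it by "Addition of week\*treatment interaction in SAS model statement".

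No model has a baseline-by-week term. The only baseline interaction considered is with treatment: "The interactions of site-by-treatment and baseline-by-treatment will be investigated separately in the model". SAP 12.4.1 drops even that for the other efficacy endpoints. On covariance, "An unstructured (UN) covariance will be assumed", with AR(1) as the first fallback.

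SAP 1.0 justifies replacing the protocol's ANCOVA partly because the MMRM "assesses missing data using the Missing at Random (MAR) assumption", and it makes multiple imputation optional. SAP 8.0 reads "Based on an estimated attrition rate of 25% after 6 months and 50% after 52 weeks" and uses this to size the GSP 301 arm for exposure. Neither document gives a placebo attrition rate, a link between dropout and symptoms or baseline, or a baseline slope.

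For PNSS, RCAT and the RQLQ(S) Analysis Set, SAP 12.4.2.4 prescribes an analysis "using the same methods as described in Section 12.3.2.2". The code in 12.3.2.2 has no treatment-by-week term, yet the PNSS and RCAT shells (T14.1.9.19.2, T14.1.9.22.2) footnote a week-by-treatment interaction.

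**The concern.** A 4-day run-in average, or one questionnaire at Visit 2, may well predict scores a few weeks later better than scores a year later. A single slope is then a compromise that is wrong at both ends.

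With complete data this hardly matters, because randomization balances baseline between arms. With dropout, the MMRM in effect predicts the missing late scores from earlier scores and baseline, and likelihood inference under MAR needs a correct mean model. A wrong slope distorts those predictions. If the subjects still observed late differ in baseline between arms, the error does not cancel in the treatment difference.

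At stake are overall RQLQ(S) at Weeks 30 and 52, a named secondary endpoint, and the weekly curves that show whether the effect lasts. Under the protocol's ANCOVA, models fitted separately at each time point would each have had their own slope. The SAP does not say that the switch to MMRM gives this up.

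**Working it through.** **1. The plan's own figure.** 300/(1 - 0.25) = 400 and 100/(1 - 0.50) = 200, so 400 is the binding number. It leaves 400 x 0.75 = 300 subjects at 6 months and 400 x 0.50 = 200 at 52 weeks. The SAP figure is reproduced.

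**2. What sets the sign.** As a rough guide to sign only, the bias at week t behaves like (true slope at t - common slope) x (GSP 301 minus placebo mean baseline among subjects still observed at t). It vanishes if either factor is zero. It reverses if either factor changes sign. The slopes below are for change, and the score slope is the change slope + 1, so a falling score slope is a steepening change slope.

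**3. Simulation inputs.** From the documents: 400 v 100 subjects, 50% GSP 301 attrition at Week 52, unstructured covariance, 95% intervals, and a true difference of -1.17 (the Phase 2 rTNSS result in Protocol 5.4). The Phase 2 interval implies SE = (1.7315 - 0.6090)/(2 x 2.2414) = 0.250, and SD = 0.250 x sqrt((1111/7)/2) = about 2.23 if its seven arms were equal (assumption).

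Assumed, with no source in the documents: baseline SD 1.8, residual SD 2.0, the dropout rules, and slopes of change at Weeks 6/30/52 that are constant (-0.45), steepening (-0.25/-0.45/-0.60) or flattening (-0.60/-0.45/-0.25). Site and the second placebo arm were left out. Bias was measured with 400,000 subjects per arm.

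**4. Bias of the common-slope, three-visit model** (negative favours GSP 301):

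| Slope | Dropout | Week 30 | Week 52 |
|---|---|---|---|
| Constant | any MAR rule | about 0 | about 0 |
| Changing | random 50%/50% or 50%/65%, or same baseline rule in both arms | about 0 | about 0 |
| Steepening | severe-baseline subjects leave placebo | -0.07 | -0.20 |
| Steepening | mild-baseline subjects leave placebo | +0.07 | +0.19 |
| Flattening | severe-baseline subjects leave placebo | +0.05 | +0.22 |
| Flattening | mild-baseline subjects leave placebo | -0.06 | -0.23 |
| Steepening | last score, same rule in both arms (placebo attrition 62-64%) | within 0.02 | -0.03 to -0.05 |
| Flattening | last score, same rule in both arms (placebo attrition 62-64%) | within 0.02 | +0.03 to +0.04 |

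Opposite baseline-related dropout in the two arms gave up to about +/-0.14 at Week 30 and +/-0.44 at Week 52. With `baseline*week`, bias was within about 0.015 of zero in every MAR case. A 14-time-point proxy for the weekly model gave the same pattern.

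**5. Symptom-driven dropout, other settings.** True difference -1.0, dropout on last score, completers 54% v 41%; Week 52 estimate, common slope v `baseline*week`:
- score slope 0.77 to 0.63: -1.021 v -1.001
- 0.80 to 0.55: -1.032 v -0.996
- 0.74 to 0.36: -1.067 v -1.008
- constant: identical
- rising, 0.55 to 0.80: -0.958 v -0.991

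Runs at 400 v 100 with about 55-57% v 43-44% completers gave Week 52 estimates of -1.03 to -1.09 against -1.00 to -1.01, and 2-9% in a model of 13 four-week blocks. Overall the Week 52 overstatement is 2-9% when the score slope falls; Week 30 moves less. The period-average models of 12.3.2.1 and 12.3.2.2 shift by at most 1.6%.

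**6. Size beside the standard error** (600 trials of 400 v 100, severe-baseline subjects leaving placebo). Steepening: Week 52 bias -0.187, SE 0.285, ratio 0.66. Expected coverage is Phi(1.96 - 0.66) - Phi(-1.96 - 0.66) = 0.90; simulated 0.898. Flattening: +0.205/0.285 = 0.72, expected 0.89, simulated 0.882. With `baseline*week`, coverage was 0.945 and 0.940. Under last-score dropout it was 0.957 and 0.935 with the common slope, and 0.960 and 0.937 with the added term.

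**7. Outside MAR.** With dropout on the current unobserved score, bias of about +0.07 (Week 30) and +0.11 (Week 52) remained after adding the term. In the steepening case the term moved Week 52 from +0.09 to +0.12.

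**The case against.** The strongest reply is that every condition for bias is assumed. The 50% is a planning figure for GSP 301 exposure, not a statement about who leaves. That stands. A reader might infer that the planned attrition makes the late effects look too favourable to GSP 301. The documents do not support this: attrition alone gave no bias, and the sign turns on a slope trend and a dropout pattern that they do not state. A falling score slope is the more natural expectation, and the disposition shell lists lack of efficacy as a termination reason, but neither settles the matter.

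Second, under symptom-driven dropout by one rule in both arms, the shift is small and coverage stays near nominal. With no true effect that rule leaves the arms exchangeable, so the common slope cannot create a false positive there; a simulated null case was within 0.013 of zero with coverage 0.96. This stands for that mechanism, not for baseline-related dropout that differs by arm.

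Third, few endpoints are touched. The rTNSS and iTNSS secondary endpoints are period averages and barely move, the weekly curves, PNSS and RCAT are other efficacy endpoints, SAP 6.0 states no hypotheses, and the primary objective is safety. This limits the importance.

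Fourth, Protocol 13.5 uses the discontinuation-visit RQLQ(S) score for early withdrawals, and SAP 1.0 does not list that rule as changed. If it still applies, RQLQ(S) missingness differs from the pattern simulated. The AR(1) fallback, plausible because an unstructured 52-week matrix has 52 x 53/2 = 1378 parameters, and the effect of rescue medication on dropout were not simulated either.

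**Conclusion.** The point holds in conditional form. The models impose one baseline slope while carrying the missing-data handling. Bias needs both a slope that changes over time and dropout that leaves the arms with different baseline mixes, and it can go either way.

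With a falling score slope and symptom-driven dropout heavier on placebo, the Week 52 difference is overstated by about 2-9% and Week 30 by less, against a Week 52 SE of about 0.25-0.3. Where baseline-related dropout differs by arm, bias of about 0.2 and coverage of 0.88-0.90 are possible. The slopes, SDs and dropout rules behind these figures are assumptions.

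It would also be too strong to infer that the added term cures dropout bias in general: it removes this source under MAR and leaves MNAR bias in place. This is a cheap improvement to secondary and other efficacy analyses, not a threat to the trial's primary conclusions.

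**What to change.** Before unblinding, append `baseline*week` to the MODEL statement in SAP 12.3.2.3, 12.4.2.2 and 12.4.2.3, with LS means taken at the overall mean baseline.

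In 12.4.2.4, first reconcile the reference to 12.3.2.2, which has no treatment-by-week term, with the PNSS and RCAT shells, which state one. Then add `baseline*week` there and in 12.4.2.5, which builds on it, and update the shell footnotes. If the term is not added, the SAP should say why.

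The cost is 3 - 1 = 2 extra parameters in the three-visit models and 52 - 1 = 51 in the 52-week models. No new data are needed, and when the slope is constant the term leaves the estimates essentially unchanged.
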